12. INVESTIGATIONAL MEDICINAL PRODUCT

Acthar Gel is a naturally sourced complex mixture of ACTH analogs and other pituitary peptides in 16% gelatin for intramuscular or SC injection. Acthar Gel contains 0.5% phenol, not more than 0.1% cysteine (added), sodium hydroxide and/or acetic acid to adjust pH, and water for injection. Acthar Gel is obtained from processing porcine pituitary using an FDA approved process. Sarcoidosis is an approved indication for Acthar Gel ([Mallinckrodt ARD LLC, 2019](#)).

Placebo is a sterile preparation of 16% gelatin for intramuscular or SC injection. Placebo contains 0.5% phenol, not more than 0.1% cysteine, sodium hydroxide and/or acetic acid to adjust pH, and water for injection. The placebo formulation is identical to Acthar Gel except that it contains no active medication.

12.1. Methods of Assigning Subjects to Treatment Groups

12.1.1. Randomization

Subjects will be randomized according to computer-generated allocation scheme to receive either Acthar Gel 1 mL (80 U) or placebo 1 mL administered 2×/week. Both investigators and the subjects will be blinded to the treatment assignment. A block randomization will be performed. The biostatistician will decide on the details at the time of the creation of the randomization scheme.

12.1.2. Interactive Telephone/Web Response System

The investigator or designee will contact IXRS to register subjects at Screening (Visit 1). The subject's identification number (ID) will be determined by the IXRS and will be used to identify the subjects for the duration of the study within all systems and documentation. Subject identification numbers will consist of 7 digits: the first 4 digits reflect the site number assigned to the Investigator and the last 3 digits are the subject number.

A subject ID number will not be assigned to more than 1 subject. If a subject is not eligible to receive treatment, or should a subject discontinue from the study, the subject ID number cannot be reassigned to another subject.

In the event that a subject is rescreened within the screening window, they do not need a new subject ID number. At the Randomization Visit, qualified subjects who meet all of the eligibility criteria will be randomized into the study.

The investigator or designee must contact the IXRS to report a subject as a screen failure if the subject does not meet eligibility criteria prior to randomization.

The investigator or designee must contact IXRS to record each subject visit, to receive the IMP assignments, and to report any subject status changes.

The investigator must maintain a subject master log linking the subject ID to the subject's name. The investigator must follow all applicable privacy laws in order to protect a subject's privacy and confidentiality. Information that could identify a subject will be masked on material received by the sponsor.

12.2. Identification of Investigational medicinal product

When knowledge of the IMP assignment is required for the medical management of an individual subject, the investigator may obtain the treatment assignment of the subject experiencing the AE or SAE. The treatment blind for that subject may be broken by accessing the IXRS using instructions provided in the Study Operations Manual. The investigator must notify the sponsor's MM or physician designee before unblinding, if at all possible, or immediately after unblinding the treatment assignment. The investigator and sponsor should make every effort to document and limit the subjects who are unblinded to the treatment assignment. The investigator must also indicate in source documents that the blind was broken and provide the date and reason for breaking the blind.

12.3. Dosing Procedures

Both Acthar Gel and placebo are supplied as 5 mL multidose vials. Acthar Gel vials contain 80 U of ACTH per mL. Vials will be labeled according to all applicable national and local regulations.

The vials should be warmed to room temperature before using. The vials should not be over pressurized; assure that no excess air (beyond the volume of product to be withdrawn) is inserted into the vial prior to withdrawing the product. After use the vial should be returned to refrigeration.

Subjects or their caregivers will administer SC injections of Acthar Gel or placebo after randomly assigned to treatment at Visit 2. The subject or subject's caregiver will administer the first dose of study drug and the first dose of Acthar Gel in the Open-Label at Week 24 in the clinic under the supervision of study staff. The subject will remain in the clinic for at least 1 hour postdose to monitor for allergic or anaphylactic reactions. All other doses will be administered by the subject or the subject's caregiver at home, but no dose should be administered on study visit days.

IMP cannot be taken on 2 consecutive days and cannot be taken more than 3 days apart. Therefore the following dosing schedule should be recommended to subjects at Visit 2, dose administration on either Monday and Thursday, Tuesday and Friday, or Wednesday and Saturday, and would be determined by the day of the week Visit 2 occurred.

In the double-blind treatment period Acthar Gel, 1 mL (80 U) or matching placebo (1 mL) will be administered twice weekly SC for up to 24 weeks. In the optional open-label extension, Acthar Gel 1 mL (80 U) will be administered SC twice weekly for up to 24 weeks. If a dose reduction of IMP is deemed necessary, a reduction of 50% (40 U) may be implemented once during the study based on safety criteria previously defined (see [Section 8.1](#)). The justification for dose reduction will be captured in the eCRF.

Subjects who, despite dose reduction, continue to experience any of the AE defined in [Section 8.1](#), will be withdrawn from the study due to AE.

Subject who required dose reduction (50%) will inject 40 U (0.5mL) throughout the study, including during the optional Open-label Extension Phase, if applicable.

12.3.1. Treatment Discontinuation

Should any of the following occur, treatment with IMP may be reduced once by 50% ([Section 8](#)) or should be discontinued:

- Development of accelerated hypertension (defined as systolic blood pressure ≥ 180 mm Hg and/or diastolic blood pressure ≥ 100 mm Hg) that cannot be managed by the adjustment of concomitant medications such as antihypertensive medications.
- Development of congestive heart failure (Class III or IV) that cannot be managed by the adjustment of concomitant medications such as diuretics and antihypertensive medications.
- Development of uncontrolled diabetic signs/symptoms that cannot be managed by the adjustment of concomitant medications such as insulin and oral hypoglycemic agents.
- Development of any other AE of at least moderate intensity and possibly, probably or definitely related to IMP that cannot be managed by the adjustment of concomitant medications.

If the subject is withdrawn due to an AE, all efforts should be made to complete end-of-treatment procedures (Visit 8, [Section 11.5](#)) as soon as deemed possible and follow-up procedures (Visit 12, [Section 11.9](#)). If applicable, the suitability of subject continuing into the optional Open-label Extension Phase will be determined by the investigator.

12.4. Storage of Clinical Supplies

Acthar Gel and placebo will be maintained in a temperature controlled, secure locked area with restricted access at the study site.

Both Acthar Gel and Placebo will be supplied in kits containing the appropriate amount of vials. Both Acthar Gel and placebo will be stored under refrigeration between 2° to 8°C (36° to 46°F). Please refer to the Pharmacy Manual for complete information regarding storage and accountability of IMP.

12.5. Drug Accountability

In accordance with US FDA and ICH requirements, the investigator will, at all times, be able to account for all IMP furnished to the study site. A drug accountability record will be maintained for this purpose. The investigator must maintain accurate records indicating dates and quantity of IMP received, to whom it was dispensed (subject-by-subject accounting) and accounts of any IMP accidentally or deliberately destroyed. All unused IMP not involved in immediate subject dosing will be maintained under locked, temperature-controlled storage at the study site.

12.6. Compliance Monitoring

Prior to beginning the administration of IMP, subjects and/or their caregiver will be trained on dosing and SC injection, and must exhibit proper technique of SC administration during initial IMP administration at Visit 2. Subjects and/or their caregiver will be trained on the

completion of the study diary and will complete study diary entries to record all study drug administration and will bring it, along with all study drug kits including used vials to each visit. Used and unused vials will be inspected. Number of expected, administered doses and reason for discrepancies will be documented. Each time study drug is dispensed compliance will be encouraged. Subject diary training is an ongoing process as the diary will be reviewed with the subject at each visit to monitor compliance with study drug administration.

13. EFFICACY ASSESSMENTS

Efficacy will be evaluated using a combination of measures including: patient reported outcomes, imaging, PFT, and corticosteroid tapering. Detailed description of efficacy assessments is provided in [Section 7.2](#).

14. SAFETY ASSESSMENTS AND PROCEDURES

Overall safety will be determined by the incidence, severity and relationship of AEs, physical examinations, vital signs, clinical laboratory abnormalities, and imaging. All safety assessments will be performed at times outlined in the Schedule of Study Events ([Table 1](#)). Additional (unscheduled) safety assessments may be performed as needed.

14.1. Adverse Events

AEs will be recorded from signing of the ICF and followed by the investigator until the AE is resolved or stabilized or at such time as the investigator refers the subject to a nonstudy physician for follow-up treatment. Any and all safety measures (which includes standard of care activities) should be provided by the study site to the subject. Any study site follow-up should be documented.

Refer to [Section 16](#) for additional details on the handling of AEs and SAEs.

14.2. Medical and Surgical History

Medical and surgical history will be obtained at Screening (Visit 1). Medical history will include a review of the following systems: general, dermatological, respiratory, cardiovascular, gastrointestinal, genitourinary, gynecological (when applicable), endocrine, musculoskeletal, hematological, neuropsychological, immune (allergies), and head, eyes, ears, nose, and throat. Historical and current medical conditions including and date of last menstrual period for female subjects will be recorded. Occupational history will also be collected.

14.3. Physical Examination

A complete physical examination will be performed at all visits and will include evaluation of the head, eyes, ears, nose, throat, neck (including thyroid), cardiovascular system (including assessment of heart, peripheral pulses, presence or absence of edema), lungs, abdomen (including liver and spleen, bowel sounds), lymph nodes, musculoskeletal system (including spine, joints, muscles) neurological system (including cranial nerves, reflexes, sensation, strength), skin, extremities and other conditions of note. Special emphasis will be made to sarcoidosis manifestations per organ involvement.

The findings of the physical examinations will be recorded. Any changes in medical conditions, specifically new medical conditions and worsening of existing medical conditions will be recorded as AE, as appropriate.

14.4. Vital Signs

Vital signs will be obtained after the subject has been seated for 5 minutes (minimum) and will include systolic and diastolic blood pressures, pulse rate, and respiratory rate.

The investigator may perform additional unscheduled vital sign measurements to evaluate or manage a suspected AE. These unscheduled vital sign measurements should be obtained after the subject has been seated for at least 5 minutes, if possible. Unscheduled vital signs will be recorded.

The date and time for all vital sign assessments will be recorded.

14.5. Clinical Laboratory Tests

The clinical laboratory tests are listed in [Attachment 1](#). Tests should be conducted as described in the Schedule of Study Events ([Table 1](#)). All clinical laboratory tests will be done at a central laboratory facility except for urine analysis, and urine pregnancy test which will be performed at the local laboratory. Specific instructions for collection, processing, storage, and shipment of clinical laboratory samples will be provided in a separate laboratory manual, where appropriate.

Samples for serum chemistry testing for all visits will be collected under fasting conditions (at least 12 hours, drinking water is permitted). The date and time of the sample collection must be documented on the laboratory report. Investigators must review and sign laboratory reports. The clinical significance of each laboratory abnormality will be documented. New clinically significant laboratory abnormalities or clinically significant changes in laboratory values will be reported as AEs, as appropriate.

In addition:

All female subjects of child bearing potential will have a serum pregnancy test at Screening (Visit 1). Urine pregnancy tests will be done at all other visits throughout the study. Results must be available prior to dosing with IMP. Subjects with positive results will be ineligible for study entry (Visit 1 or Visit 2) or immediately withdrawn from the study (Visit 3 through Visit 11) and the pregnancy reported as per [Section 16.5](#).

HBsAg and HBcAb will be performed at Screening (Visit 1). Results of these tests must be negative or nonreactive for subjects to qualify for the study.

HCV will be performed at Screening (Visit 1). A positive HCV will automatically trigger a HCV PCR analysis. HCV PCR must be < 25 IU/mL to qualify for the study.

IGRA for TB will be performed at Screening (Visit 1). Results of this test must be negative for subjects to qualify for the study.

Out-of-Range Laboratory Values

Laboratory values from samples collected at Screening (Visit 1) will be evaluated by the investigator for eligibility of the subject in the study. Clinical laboratory tests may be repeated once to determine subject eligibility.

Laboratory values from scheduled or unscheduled laboratory assessments that fall outside the reference range from samples collected during the study or at study exit or early discontinuation will be assessed by the investigator for clinical significance. If the out of range value for samples is deemed clinically significant by the investigator, an AE will be recorded.

14.6. 12-Lead Electrocardiogram

Electrocardiogram will include assessment of sinus rhythm, heart rate, PR Interval, RR Interval, QRS Duration, Q-T Interval and QTcB.

A 12-lead ECG will be obtained for all subjects at Screening (Visit 1) and Visits 8 and 11. The date of the ECG must be documented on the ECG tracing. An appropriately trained and experienced physician must interpret this ECG. Date, time, and clinical parameters from the

all ECGs will be entered in the eCRF. At the discretion of the investigator a repeat ECG may be collected at the screening visit to confirm findings.

Additional ECGs may be performed any time throughout the study if deemed clinically necessary and entered into eCRF.

15. STATISTICAL METHODS AND PLANNED ANALYSIS

15.1. General Considerations

This section provides a general description of the statistical methods to be used in analyzing both safety and efficacy data. The key statistical issues or considerations will be addressed in more detail in a statistical analysis plan to be provided as a separate document that will be finalized prior to database lock. The analyses for the double-blind phase data will be performed after the database lock for the double-blind phase.

Unless otherwise specified, all statistical tests, when applicable, will be 2-sided with a significance level of 0.05. Summary statistics will be provided for all study variables with descriptive statistics (number of observations, mean, SD, median, minimum, and maximum) for numerical (or continuous) variables. Frequency and percentages will be calculated for categorical variables. All data will be summarized by treatment groups as appropriate. Data summary and analyses will be performed with SAS 9.4 or higher.

15.2. Analysis Populations

The following populations will be identified and analyzed in this study:

A Modified Intent-to -Treat (mITT) Population that includes all randomized subjects who receive at least 1 dose of IMP and who contribute any efficacy data to the study will be used for the efficacy analyses. A Safety Population that includes all randomized subjects who receive at least 1 dose of IMP will be used for all the safety analyses.

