The first study was a retrospective chart review of 47 patients with advanced sarcoidosis seen at 2 clinical centers who received at least 1 dose of Acthar Gel with at least 6 months of posttreatment follow-up. All patients initially received Acthar Gel 80 U intramuscular or SC administration twice a week (2×/week). Eighteen patients (37%) discontinued drug within 6 months due to study participation cost (4 patients), death (2 patients), or drug toxicity (11 patients), or noncompliance (1 patient). Of the remaining 29 patients, 11 experienced objective improvement in 1 or more affected organs. All but 2 patients noted disease improvement or oral glucocorticoid reduction. Twenty-one patients were treated for more than 6 months (median 274 days). Nineteen patients were taking prednisone at time of starting Acthar Gel: 17 had their prednisone dosage reduced by more than 50%, and 1 patient discontinued cyclophosphamide therapy. Acthar Gel treatment for at least 3 months was associated with objective improvement in a third of the patients. A third of the patients were unable to take treatment for at least 3 months ([Baughman et al., 2016](#)).

The second study was a prospective study of 16 patients with chronic pulmonary sarcoidosis receiving prednisone therapy with deterioration by at least 5% in FVC in the previous year. Acthar Gel was administered at a loading dose of 80 U SC for 10 days. Patients were randomized at Day 14 to receive either 40 U or 80 U Acthar Gel 2×/week for 24 weeks. The dose of prednisone was modified by the clinician who was blinded to the patient's dosage of Acthar Gel. At Week 24, there was a decrease in the dose of prednisone and improvements in DLCO, the King's Sarcoidosis Questionnaire (general health status), and the Fatigue Scale. There was no significant change in FVC % predicted. For the positron emission tomography scan, there was a significant fall in the standard uptake value of the lung lesions. Only 3/8 patients remained on 80 U repository corticotropin for full 24 weeks. There was no significant difference in the response to therapy for those treated with 40 U vs 80 U Acthar Gel. The authors concluded that Acthar Gel treatment was prednisone-sparing and associated with significant improvement in DLCO, positron emission tomography scan, and patient-reported outcome measures. A dose of 40 U repository corticotropin 2×/week was as effective as 80 U Acthar Gel and was better tolerated ([Baughman et al., 2017](#)).

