8. STUDY DESIGN

8.1. Description

This is a multicenter, randomized, double-blind, placebo-controlled exploratory study evaluating the efficacy and safety of Acthar Gel in the treatment of pulmonary sarcoidosis.

The study will have 3 phases: Screening (up to 28 days); double blind treatment (24 weeks); and an optional open-label, 24 weeks extension. A follow-up visit will be conducted 4 weeks (\pm 2 days) after the last dose of IMP is administered.

Following signature of the ICF and a screening period of up to 28 days, subjects who meet all eligibility criteria will be randomly assigned to receive either 1 mL (80 U) of Acthar Gel or 1 mL of a matching placebo SC 2 \times /week. Subjects will be assigned to treatment in a 1:1 ratio with up to 50 subjects per arm for a total of approximately 100 subjects.

Dose reduction of 50% may be implemented once during the study, if a subject meets one of the following prespecified safety criteria based on clinical judgment:

- Uncontrolled hypertension (newly developed or worsening of existing hypertension) before/or in conjunction with addition/adjustment of antihypertensive therapy.
- Uncontrolled diabetic signs/symptoms (newly developed or worsening of existing diabetes) before/or in conjunction with addition/adjustment of antihyperglycemic therapy.
- Unacceptable toxicity defined as any AE of at least moderate intensity not adequately controlled by concomitant medication use or other non IMP-related measure

The justification for dose reduction will be captured in the eCRF. Subjects will remain on the 40 U or matching placebo 2 \times /week for the remainder of the study. Subjects who, despite dose reduction, continue to experience any of the above mentioned AEs, (meet a criteria as above) or experience another event will be withdrawn from the study due to AE ([Section 12.3](#)).

Subjects will be followed every 4 weeks (\pm 5 days) for 24 weeks (Visit 2 to Visit 8). During each visit following Visit 2, steroid tapering evaluation will occur based on the corticosteroid tapering algorithm ([Section 7.2.4](#)). A justification for any deviation will be captured in the eCRF.

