11.2. Visit 2 Procedures

The investigator or designee will complete the following procedures at Visit 2:

- Inclusion/exclusion criteria review.
- Spirometry (ascertain any difference in FVC < 10% compared with FVC performed at Visit 1 before continuing).
- Vital sign determinations Vital signs will be obtained after the subject has been seated for 5 minutes (minimum) and will include systolic and diastolic blood pressures, pulse rate, and respiratory rate (see [Section 14.4](#)).
- Weight measured. Every effort should be made for weight to be measured by the same calibrated scale at every visit.
- Physical examination (see [Section 14.3](#)). The full physical examination will include a targeted examination of the organ involved. All efforts must be undertaken for the same physician to perform the physical examination (per organ involved) at each visit.
- ePOST: All efforts must be undertaken for the same physician to perform the ePOST ([Attachment 3](#)) side-by-side with prior evaluations.
- Physician Global Assessment ([Attachment 7](#)).
- Patient reported outcomes and assessments. Patient-reported outcomes include: Steroid toxicity questionnaire; King's Sarcoidosis Questionnaire ([Attachment 4](#)); Fatigue Assessment Scale ([Attachment 5](#)); Patient's Global Assessment ([Attachment 6](#)); Medical Research Council Dyspnea Scale ([Attachment 8](#)); Leicester Cough Questionnaire ([Attachment 9](#)), WPAI ([Attachment 10](#)).
- Clinical laboratory tests:
 - Complete blood count.
 - Clinical chemistry including liver function tests (samples will be collected from subjects who have been fasted for at least 12 hours. Drinking water is allowed).
 - HbA1C.
 - Human chorionic hormone (urine pregnancy testing, females of child bearing potential only [performed at a local laboratory]).
- Injection and diary training (if additional training is required).
- Contact IXRS to randomize subject and dispense study drug kits.
- Dosing will begin after Visit 2 procedures are completed and subject is randomized. Subjects (and/or caregivers) will be trained on SC injections and diary

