11.10. Early Termination Procedures

Subjects who discontinue participation for any reason prior to Visit 8 or Visit 11 will have the procedures listed for Visit 8 completed as soon as possible. The reason for discontinuation should be documented in eCRF. Unused medication and study supplies will be collected from the subjects. Subjects should also return to complete the follow-up procedures during Visit 12.

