4.1. Sample Size

Formal sample size calculations were not performed. The sample size is based on recent literature of comparative studies ([Gibson et al., 1996](#); [Baughman et al., 2006](#); [Judson, 2014](#)) in sarcoidosis. There are 55 subjects randomized to this study.

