4.4. Analysis Populations

4.4.1. Modified Intent-to-Treat Population

The modified Intent-to-Treat (mITT) Population includes all randomized subjects who receive at least 1 dose of IMP and who contribute any efficacy data to the study. The mITT Population will be used for the efficacy analyses based on the treatment they actually received during double-blind treatment phase.

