vs. non-responder rate. At 48 weeks (Visit 11) during open-label phase, the proportions of STS responder and non-responder along with 95% CI will be provided. The 95% CI will be calculated by using the exact (Clopper-Pearson) method.

Missing STS scores will be imputed at 24 weeks (Visit 8) during double-blind treatment phase. Last observation carried forward (LOCF) method will be employed to impute missing component(s) if any component of STS is missing at the post-baseline visit during double-blind treatment phase. If there is still missing component(s) after applying LOCF imputation method, STS score will remain as missing. Subjects who do not provide data (after component level LOCF imputation) to allow classification as responders will be considered non-responders, that is, missing data will be imputed as non-responder. The same missing data imputation method will be applied to other similar efficacy endpoints in double-blind treatment phase. No imputation will be applied to the open-label extension phase. A bar plot of STS category will be provided at 24 weeks (Visit 8) during double-blind treatment phase and at 48 weeks (Visit 11) during open-label phase, respectively.

Sensitivity analyses with using only the observed data will be performed for the above analysis at 24 Weeks (visit 8) only.

Subgroup analyses by sex, race and ethnicity will be performed in similar manner as specified above on the imputed data only.

STS component scores including FVC % Predicted Score, DLCO % predicted Score, HRCT Score, King's Sarcoidosis Questionnaire (KSQ) General Health Score, Fatigue Assessment Score and Corticosteroid Taper Score will be summarized. Number and percentage of subjects in each category (Improved, Unchanged and Deteriorate) of each STS component score presented in Table 1 will be provided at 24 weeks (Visit 8) and at 48 weeks (Visit 11). Pearson's chi-square test (or Fisher's exact test if any expected count is less than 5) will be used to assess the comparability between treatment groups for each STS component at 24 Weeks (visit 8) only.

Listings of STS components and STS scores will be provided by study phases. Subjects with any missing component of STS will be indicated.

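### The mITT definition does not say whether baseline data count as efficacy data; on the stricter reading, some dosed early leavers escape the SAP's own missing-equals-failure rules.

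*Protocol*

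**What the plan says.** Protocol 15.2 defines the modified intent-to-treat (mITT) population as "all randomized subjects who receive at least 1 dose of IMP and who contribute any efficacy data to the study", and SAP 4.4.1 repeats the definition. The SAP adds: "The mITT Population will be used for the efficacy analyses based on the treatment they actually received during double-blind treatment phase". The Safety Population (protocol 15.2, SAP 4.4.2) has the dose condition only. Neither document says whether the efficacy data must be post-baseline.

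SAP section 9 runs double-blind efficacy on the mITT set unless otherwise specified. For that phase the SAP treats missing data as failure:

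- **STS at Week 24 (SAP 9.1):** "Subjects who do not provide data (after component level LOCF imputation) to allow classification as responders will be considered non-responders".
- **Willingness to continue treatment (SAP 9.2):** a missing answer becomes a No.
- **FVC and DLCO improvement thresholds (SAP 9.3):** mITT subjects without an evaluable assessment count as not improved.
- **HRCT and CXR (SAP 9.4.1):** a missing reading takes the unfavourable category.

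The only STS sensitivity analysis uses observed data (SAP 9.1).

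On timing, protocol 11.2 states: "Dosing will begin after Visit 2 procedures are completed and subject is randomized". After that, "Subjects will be followed every 4 weeks" (protocol 8.1), so the first scheduled post-baseline visit is Week 4. Subjects who discontinue early "will have the procedures listed for Visit 8 completed as soon as possible" (protocol 11.10). Protocol 12.3.1 and 17.1 likewise call for those assessments after withdrawal.

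**The concern.** The efficacy-data condition has two readings, and the plan does not choose between them. On one it does nothing, and two separately named populations are the same. On the other it selects subjects by something that happens after randomisation, namely whether they stayed or returned long enough to give a post-baseline measurement.

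The second reading works against the SAP's missing-data rules. Someone who gives one Week 4 questionnaire and then leaves is a non-responder. Someone who leaves earlier and never returns is not counted. If that happens more often in one arm, that arm's response rate rises relative to the other.

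At stake are the Week 24 STS responder comparison, the continue-treatment comparison, the FVC and DLCO improvement rates and the imaging categories. The protocol's background makes early stopping on the active drug a fair question. Of 47 patients in a retrospective review, 11 stopped for toxicity within 6 months, and "A third of the patients were unable to take treatment for at least 3 months". In a small prospective study, 3 of 8 stayed on 80 U for the full 24 weeks.

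**Working it through.** **Step 1: what each reading does.** Questionnaires, global assessments and ePOST are collected at Visits 1 and 2, full pulmonary function tests at Visit 1, and spirometry at Visit 2 (protocol 11.1 and 11.2). All precede the first dose.

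| Reading | Who is excluded | Effect |
|---|---|---|
| Baseline data count | Essentially no dosed subject | mITT equals Safety Population; failure rules reach everyone |
| Post-baseline data required | Dosed subjects with no Week 4 data and no early-termination assessment | These subjects escape the failure rules |

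**Step 2: inputs for an illustration.** The plan has no power calculation or assumed response rate to reproduce. From the documents: "There are 55 subjects randomized to this study" (SAP 4.1), 1:1 allocation (SAP 4.2), two-sided 0.05 (protocol 15.1, SAP 4.3), and Pearson chi-square unless an expected count is below 5 (SAP 9.1). Assumed: 27 Acthar and 28 placebo subjects, all dosed, since arm sizes are not given; the response counts; and 1 to 4 Acthar exclusions, all non-responders.

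**Step 3: effect on a rate.** Excluding k non-responders from n subjects with r responders changes the rate from r/n to r/(n−k). With n=27:

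| True rate over all dosed | k=1 | k=2 | k=3 | k=4 |
|---|---|---|---|---|
| 40% (r=10.8) | 41.5% | 43.2% | 45.0% | 47.0% |
| 50% (r=13.5) | 51.9% | 54.0% | 56.2% | 58.7% |

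**Step 4: effect on a borderline test.** For responders a and c and non-responders b and d in the two arms, χ² = N(ad−bc)² / (product of the four margins), without continuity correction.

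- No exclusions, 13/27 v 7/28: 55×(13×21−14×7)²/(27×28×20×35) = 55×175²/529,200 = 3.183, p=0.074.
- One Acthar exclusion, 13/26 v 7/28: χ²=3.613, p=0.057.
- Two Acthar exclusions, 13/25 v 7/28: 53×189²/462,000 = 4.098, p=0.043.
- Three Acthar exclusions, 13/24 v 7/28: 52×196²/430,080 = 4.645, p=0.031.
- Two exclusions in each arm, 13/25 v 7/26: 51×163²/403,000 = 3.362, p=0.067.

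Every expected count exceeds 9, so Pearson's test applies throughout.

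**Step 5: false-positive rate.** This uses the other possible split, 28 Acthar and 27 placebo, with equal true rates p₀ over all dosed subjects. The retained Acthar subjects then respond at p₀×28/(28−k). Exact enumeration of the two binomials gives:

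| p₀ | k=0 | k=1 | k=2 | k=3 | k=4 |
|---|---|---|---|---|---|
| 30% | 0.048 | 0.055 | 0.053 | 0.062 | 0.070 |
| 40% | 0.054 | 0.047 | 0.059 | 0.059 | 0.082 |
| 50% | 0.058 | 0.044 | 0.063 | 0.073 | 0.095 |

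One one-sided exclusion makes no consistent difference. Three or four raise the error.

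**The case against.** A reader might infer that the mITT definition drops the earliest leavers and so inflates the Acthar response rate. The documents do not support that:

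- **The wording does not say post-baseline.** Read literally, a baseline questionnaire is efficacy data, and practically every dosed subject stays in. Two populations that coincide are redundant, not wrong.
- **Early leavers should still be assessed.** It is tempting to say that someone who stops for toxicity on Day 10 is not counted. Protocol 11.10, 12.3.1 and 17.1 call for the Visit 8 assessments after early withdrawal. A Day 10 stopper who attends has post-baseline data and is in the mITT on either reading.
- **The background gives no rate before Week 4.** Its figures are for 3 and 6 months. Many of those patients would have passed Week 4 and would count as failures here. The 47-patient series is a retrospective chart review, and 4 of its 18 discontinuations were for cost.
- **The illustration is chosen near the threshold.** One exclusion does not cross it, and equal exclusions largely cancel. The trial is exploratory, without a formal sample size calculation.
- **Exclusions would be visible.** SAP section 5 tabulates the populations and early-termination reasons by arm.

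All of this stands, and it limits the point to an unresolved definition with a possible bias. It does not settle which reading applies. A table of population counts would reveal exclusions without correcting the comparison.

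**Conclusion.** The concern holds as an ambiguity in the efficacy denominator. On the literal reading nothing changes. On the post-baseline reading, dosed subjects who leave before Week 4 and miss the early-termination assessments fall outside the failure rules, and the observed-data sensitivity analysis cannot restore them.

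The size depends on how many such subjects there are and in which arm, and the documents give neither. Under the assumptions above, two or three Acthar-only exclusions could carry a borderline result across 0.05. An established inflation in favour of Acthar cannot be claimed: more early stopping on active drug is plausible from the background, but stopping alone removes nobody from the mITT. The change is still worth making, because the condition is either idle or contrary to the SAP's own rules.

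**What to change.** In protocol 15.2 and SAP 4.4.1, delete the condition about contributing efficacy data, so that the efficacy set is all randomised subjects with at least one dose of IMP. Responder-type endpoints then use that set, with missing data counted as failure under SAP 9.1, 9.2, 9.3 and 9.4.1 as already written. Continuous analyses that need a post-baseline value are unaffected.

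If the condition is kept, state whether baseline-only data satisfy it, and report the number and reason for each mITT exclusion by arm.

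The cost is one clause in each document and no new data. If the literal reading was intended, no result changes. Otherwise, reported response rates stay the same or become slightly lower.
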